## **Revision History**

Revision	Date Issued	ECO
A	April 22, 2021	
В	May 10, 2021	
С	September 30, 2021	

## **1 PROTOCOL SYNOPSIS**

Protocol Title	An Observational Multicenter Clinical Study to Assess the Safety and Effectiveness of the OMNI ® Surgical System in Pseudophakic Eyes with Primary Open Angle Glaucoma	
Investigational Device	OMNI ® Surgical System	
Study Objective		
Study Design	This is a multicenter, observational research study with no planned surgical interventions. Both prospective and retrospective data on participating subjects will be collected in the study.	
Primary Safety Endpoint	1. Rate of occurrence of sight-threatening adverse events (AEs)	
Secondary Safety Endpoints	
 
Rate of ocular AEs
 
Reduction in best corrected distance visual acuity (BCVA) from baseline
 
Secondary Surgical Interventions, including laser, for IOP control
 
	
Effectiveness Endpoints		

Rev C

Number of Subjects Enrolled and Treated	Up to 100 subjects. Up to 50 subjects who received OMNI intervention post medication washout and up to 50 subjects who received OMNI intervention without medication washout will be enrolled
Number of Sites	Up to 15 study sites in United States.
Schedule of Visits	
 
The following visits will be captured retrospectively: 
 
Subjects with preoperative medication washout: Pre-washout, Post-washout, Surgical
 
Subjects without a medication washout: Preoperative, Surgical
 
 
 
The following visits will be captured prospectively: 
 
Months 6*, 12*, 18 and 24.
 
 
 
Subjects with a preoperative washout will also undergo washout for the 12-and 24- month visits if they are on ocular hypotensive medication at these visits and return for an exam following appropriate washout period.
 
* The 6- and 12-month data can be retrospective or prospective depending on date of enrollment.
 

Interim analysis	100% subjects reaching 12 Month visit

### 2 STUDY OBJECTIVE

The purpose of this study is to evaluate the safety and effectiveness of the OMNI® Surgical System in subjects who have undergone canaloplasty and trabeculotomy using OMNI® Surgical System without any concomitant surgery in pseudophakic eyes with mild to moderate primary open angle glaucoma (POAG) at least 150 days prior to enrollment.

### **3** BACKGROUND AND JUSTIFICATION FOR THE STUDY

Glaucoma is a progressive disease leading to irreversible damage to retinal ganglion cells with the global burden expected to rise to 111.8 million people by the year 2040. POAG is the most prevalent form of glaucoma and elevated IOP is the only treatable risk factor. Hypotensive eye

<sup>1 Tham YC, Li X, Wong TY, et al. Global prevalence of glaucoma and projections of glaucoma burden through 2040: a systematic review and meta-analysis. Ophthalmology. 2014;121:2081–2090.

<sup>2 European Glaucoma Society. Terminology and guidelines for glaucoma 4th edition Savona, Italy: Editrice PubliComm, 2014.

drops are commonly used as the first line clinical management for POAG. Ocular side effects such as allergies, ocular surface disorders, blepharitis, pemphigoid, abnormal pigmentation etc. and systemic side effects such as bradycardia, headaches, depression, anxiety, confusion, dysarthria, hallucinations, lethargy, polyuria, weight loss, metabolic acidosis, etc. can occur during long term use of topical medications. There is also a documented low rate of compliance with eye drops that increases the risk of disease progression and loss of vision.

The Ocular Hypertension Treatment Study showed that reduction of IOP by an average of 22.5% through medical intervention decreased conversion from ocular hypertension to glaucoma over a 5-year period to approximately half that of untreated controls (4.4 vs. 9.5%). Similarly, the EMGT showed that treatment of newly diagnosed POAG with argon laser trabeculoplasty plus betaxolol reduced the risk of disease progression at 6 years to half of that for untreated controls (hazard ratio, 0.50; 95% confidence interval, 0.35–0.71). Each mmHg of IOP reduction decreased the risk of progression by approximately 10%. AGIS showed that eyes with 100% of visits with IOP less than 18 mmHg over 6 years had mean changes from baseline in visual field defect score close to zero during follow-up.

efficacy profile in reducing IOP. Trabeculotomy is another such procedure that relieves the resistance to aqueous flow by cleaving the trabecular meshwork and the inner wall of Schlemm's canal, resulting in pressure reductions.

The OMNI® Surgical System is indicated for canaloplasty (microcatheterization and transluminal viscodilation of Schlemm's canal) followed by trabeculotomy (cutting of trabecular meshwork) to reduce intraocular pressure in adult patients with primary open-angle glaucoma.

Note: A summary of known and potential risks to humans, as identified in the literature or through preclinical testing and/or prior clinical evaluations for the study devices can be found in the Instructions for Use for the OMNI Surgical System.

This is a multicenter, observational clinical study with no planned surgical intervention. Both prospective and retrospective data on participating subjects will be collected in the study.

# 4 STUDY DEVICE

# 4.1 DEVICE DESCRIPTION

The OMNI® Surgical System is indicated for canaloplasty (microcatheterization and transluminal viscodilation of Schlemm's canal) followed by trabeculotomy (cutting of trabecular meshwork) to reduce intraocular pressure in adult patients with primary open-angle glaucoma.

The OMNI is designed to function with commonly used viscoelastic fluids made commercially available by companies such as Johnson & Johnson Vision, Bausch & Lomb, and Alcon. The OMNI dispenses fluid on the principle of exchanging volumes much like a syringe. The handheld instrument includes a cannula, microcatheter, internal reservoir and plunger tube, and finger wheels. The finger wheel on the handle of the device allows the OMNI device to be used in either eye (OD or OS) and in either hand of the surgeon (left or right), by turning the device 180 degrees along its vertical axis and is used to advance and retract the microcatheter. In addition, when the device is being used to deliver viscoelastic, retraction of the microcatheter causes the plunger tube to advance into the viscoelastic fluid reservoir thereby dispensing viscoelastic fluid.

<sup>10 Francis BA, Singh K, Lin SC, et al. op cit.

[figure not shown]
 <sup>11 Vinod K, Gedde SJ. Clinical investigation of new glaucoma procedures. Curr Opin Ophthalmol 2017;28:187–193.
  Lewis RA, von Wolff K, Tetz M, et al. Canaloplasty: circumferential viscodilation and tensioning of Schlemm canal using a flexible microcatheter for the treatment of open-angle glaucoma in adults. Two-year interim clinical study results. J Cataract Refract Surg 2009;35:814-824.

<sup>13 Sarkisian SR, Mathews B, Ding K, et al. 360°ab-interno trabeculotomy in refractory primary open-angle glaucoma. Clin Ophthalmol 2019;13:161-168.

<sup>14 Grover DS, Smith O, Fellman RL, et al. Gonioscopy-assisted transluminal trabeculotomy: an ab interno circumferential trabeculotomy: 24 months follow-up. J Glaucoma 2018;27:393-401.

The microcatheter can be advanced/retracted up to 20 mm per cycle. The microcatheter can be fully advanced/retracted up to 5 times (i.e. 5 full cycles of 20 mm each). Dispensation of viscoelastic can only occur during the first two 20-mm cycles.

The OMNI can deliver approximately 5.5 microliters of viscoelastic in each 20 mm cycle (total volume = 11 microliters).

### 4.2 TRAINING

All surgeons would have received training in accordance with Sight Sciences' requirement for using the OMNI Surgical System. OMNI surgery will not be conducted in this trial therefore study specific training on the device will not be required.

The study will employ a medication washout at the 12- and 24-month endpoints only for the subjects that received the OMNI procedure post-medication washout.

### 5.1 STUDY SITES

This clinical study will be conducted at up to 15 sites in the United States.

#### 6 STUDY ENDPOINTS

#### 6.1 PRIMARY SAFETY ENDPOINT

Rate of occurrence of sight-threatening adverse events (AEs)

#### 6.1.1 SECONDARY SAFETY ENDPOINTS

[figure not shown]
- Rate of ocular AEs
- Reduction in best corrected distance visual acuity (BCVA) from baseline
- Secondary Ocular Surgical Interventions, including laser, for IOP control

7 STUDY SELECTION CRITERIA	

Study of OMNI Syst	tem in	POAG
Protocol		Rev C

## 8 STUDY PROCEDURES

## 8.3 NUMBER OF SUBJECTS, DURATION OF FOLLOW-UP AND STUDY DURATION

Up to 100 subjects meeting eligibility criteria with a minimum of 150 days of follow-up post-surgery using the OMNI Surgical System will be enrolled in this study.

Enrollment is stratified. Up to 50 subjects will be enrolled for whom there was a presurgical washout of ocular hypotensive medications; up to 50 subjects will be enrolled for whom there was no pre-surgery washout.

It is anticipated that site initiation, data collection and site close-out will require approximately 30 months.

### 8.4 INFORMED CONSENT AND POINT OF ENROLLMENT

The pre-operative and surgery data (and in some cases, depending on enrollment date, Month 6 and Month 12) will be collected retrospectively by performing the review of medical charts. Any patients identified as meeting the study eligibility criteria will then be consented for the study for the prospective observational data collection.

The IRB-approved informed consent will be presented and explained to each prospective subject by the Investigator or a delegated, trained clinical professional. Once the subject has had ample time to read the consent form, has been informed of all aspects of the study, and has had an opportunity to ask questions, the subject will be given a choice to voluntarily confirm his or her participation in the study as documented by completion of the Informed Consent. After signing the Informed Consent and the HIPAA (Health Insurance Portability and Accountability Act) authorization, the subject can then proceed with the study visits. The subject has the right to withdraw from the study at any time without consequences, as indicated in the Informed Consent Document.

The subject's signed and dated informed consent must be obtained before conducting any study specific procedures that are not part of the standard of care.

The investigative site must retain the original, signed written Informed Consent Document. A copy of the written Informed Consent Document must be given to the subject.

## 8.5 ELIGIBILITY AND STUDY ENTRY

Subjects will be recruited from the Investigators' patient records. Eligible subjects will consist of those patients meeting all inclusion criteria and none of the exclusion criteria, and for whom the date of surgery using the OMNI Surgical System is at least 150 days prior to enrollment in the study.

- All potential subjects should be screened for enrollment, and all eligible cases will be included up to the enrollment limit for each site.
- For the subjects who received OMNI intervention after medication washout, the eye that received OMNI surgery post medication washout should be enrolled.
- For the subjects who received OMNI intervention without medication washout if both eyes qualify, the eye with higher pre-operative medicated IOP should be enrolled. If both eyes have same pre-operative medicated IOP, right eye should be enrolled.

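### Section 8.5 as published gives no rule for choosing the study eye when both eyes had OMNI after medication washout, so the choice can be made with early results in view

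*Combined protocol and SAP*

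**What the plan says.** Section 8.5 treats the two strata differently. Without washout, "if both eyes qualify, the eye with higher pre-operative medicated IOP should be enrolled", and a tie-break follows: "If both eyes have same pre-operative medicated IOP, right eye should be enrolled". With washout, the only instruction is that "the eye that received OMNI surgery post medication washout should be enrolled".

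The same section draws subjects from the investigators' own records and requires that "the date of surgery using the OMNI Surgical System is at least 150 days prior to enrollment in the study". On the visits, the synopsis says: "The 6- and 12-month data can be retrospective or prospective depending on date of enrollment". Section 8.4 repeats this for chart review, and the synopsis lists Months 18 and 24 as prospective. Section 9 also collects adverse events from surgery up to enrollment. Section 8.3 caps the washout stratum at 50 subjects, and section 10.4 analyses the two strata separately.

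**The concern.** The washout sentence decides the matter when one eye was operated after washout. When both were, each eye fits the description and nothing visible chooses between them. The adjacent bullet shows that the authors foresaw two qualifying eyes and settled that case on pre-operative data, but for one stratum only.

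In a study that enrolls before surgery this would be a missing detail. Here the person choosing the eye may already have seen how each eye fared. No bad faith is needed: any site habit that correlates with the eye's course is enough.

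At stake are the stratum's IOP and medication results and its adverse event rates, including the primary safety endpoint, because events before enrollment are collected. Section 8.9.2 wants subjects with an earlier secondary intervention enrolled and counts them as treatment failures. If one washout eye had such an intervention and the fellow eye did not, the wording of 8.5 would allow the fellow eye to be enrolled instead. Separate analysis of the strata means the other stratum would not dilute the effect.

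**Working it through.** The plan states no figure on this point, so there is none to reproduce. The check is first of the text, then of the possible size.

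**Text**

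| Situation | No washout | Washout |
|---|---|---|
| One eye qualifies | That eye | The eye operated after washout |
| Both operated, only one after washout | Not applicable | The eye operated after washout |
| Both eyes qualify | Higher pre-operative medicated IOP | No visible rule |
| Tie | Right eye | No visible rule |

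The gap is confined to subjects with both eyes operated after washout. The requirement in 8.5 to include all eligible cases governs who enters and does not name the eye.

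**Known at selection.** Always: at least 150 days of post-operative course, which can fall short of Month 6. Sometimes: Month 6 and Month 12. Never: Months 18 and 24.

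**Size for IOP, upper bound.** Suppose the site always takes the better eye on the same measure that is later analysed. For two equally variable normal values with standard deviation SD and between-eye correlation ρ, the expected better value lies below the mean by

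shift = SD × √((1 − ρ)/π).

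The documents give neither SD nor ρ. Assume SD 3 to 5 mmHg and ρ 0.3 to 0.7:

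- SD 3, ρ 0.7: 3 × √(0.3/π) = 0.93 mmHg
- SD 4, ρ 0.5: 4 × √(0.5/π) = 1.60 mmHg (a simulation of one million pairs gave 1.60)
- SD 5, ρ 0.3: 5 × √(0.7/π) = 2.36 mmHg

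These are shifts per bilateral subject. The stratum mean moves by the share f of bilateral subjects times the shift. The documents do not give f either; assume 0% to 50%:

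- f = 0: 0 mmHg
- f = 0.5: from 0.5 × 0.93 = 0.46 to 0.5 × 2.36 = 1.18 mmHg

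The range is therefore 0 to about 1.2 mmHg. The formula applies to raw IOP or to change from baseline, with SD and ρ taken for whichever measure is used.

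**Selection on early IOP.** If the eye is chosen on an early measurement and a later one of equal variability is analysed, the shift is multiplied by r, the correlation between the early and the later between-eye difference. With r = 0.5, an illustration only, 1.18 becomes 0.59 mmHg.

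**Size for an adverse event, upper bound.** With per-eye rate p and between-eye correlation φ of the event, the better-eye rate is p² + φp(1 − p). Assume p = 5% and φ 0 to 0.5:

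- φ = 0: 0.0025; at f = 0.5 the stratum rate is 0.5 × 0.05 + 0.5 × 0.0025 = 2.6%
- φ = 0.5: 0.0025 + 0.5 × 0.0475 = 0.02625; at f = 0.5 the stratum rate is 0.5 × 0.05 + 0.5 × 0.02625 = 3.8%
- f = 0: 5%, unchanged

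**The case against.** The strongest reply is that the situation may never arise. The washout sentence speaks of a single, definite eye, and only the other bullet mentions both eyes qualifying, so the authors may have expected one washed-out eye per subject. Nothing in the documents says that any subject had both eyes operated after washout. In addition, section 7 (selection criteria) appears in the public text as a heading only, and the visit schedules (8.1, 8.2) and the analysis populations (10.2) are not shown. A one-eye condition or a study-eye definition there would close the gap. Both points stand. They make this a matter to confirm first, but they do not supply a rule in 8.5.

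A second reply is that much of the outcome is still to come. This also stands in part. A reader might infer that the site knows the eye's outcome when choosing it. The documents support that only for the early course, and in some subjects for Months 6 and 12. The 24-month result, including any post-washout measurement, cannot be known.

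Third, the size is a worst case built on assumed inputs. That is correct, and it is why it is given as an upper bound with a floor of zero.

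The subject-level safeguards (screening all potential subjects, and enrolling those with an earlier re-intervention) limit selection of subjects. They do not choose the eye.

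**Conclusion.** The point holds within limits. On the visible text, a washout subject with both eyes operated after washout can be enrolled with either eye, and the choice can be informed by at least 150 days of results. The stratum mean IOP could shift by 0 to about 1.2 mmHg. That bound rests on the assumed SD, correlation and bilateral share, and on always taking the better eye on the measure analysed. A share above 50% would raise it; selection on early IOP alone would lower it.

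Three stronger readings are not supported. The gap does not arise whenever both eyes were operated, because the sentence decides if only one was operated after washout. The documents give no evidence that any site chose eyes on results. Nor would the damage be beyond repair: if fellow-eye eligibility is recorded, an analysis without the affected subjects is possible.

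The matter deserves correction because the remedy is very cheap and the affected stratum is reported on its own.

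**What to change.** First, confirm whether section 7 or another section not shown already limits washout subjects to one eligible eye. If so, a cross-reference in 8.5 is enough.

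If not, add to 8.5 a rule that uses only facts fixed before any outcome, for example: *If both eyes received OMNI after washout and both qualify, enroll the eye with the higher post-washout pre-operative IOP; if equal, the right eye.* The synopsis lists a post-washout visit, so the value should be in the chart, and the rule matches the other stratum. Taking the first-operated eye, then the right eye, is also acceptable. Either rule removes selection on post-operative results. The higher-IOP rule leaves some regression to the mean in change from baseline, as it already does in the no-washout stratum; the first-operated rule does not select on that measurement directly.

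Record on the CRF whether the fellow eye also qualified, and report how many subjects had two eligible eyes. For subjects already enrolled, report a sensitivity analysis excluding those with two eligible eyes.

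The cost is one sentence, one CRF field and a small additional analysis, which will be less precise because it uses fewer of the at most 50 subjects.

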#### **10.4** EFFECTIVENESS ENDPOINTS AND ANALYSIS METHODS

Descriptive statistics on continuous variables will include mean, standard deviation, median, minimum, and maximum. Confidence intervals for change from baseline will be included for selected endpoints. Categorical variables will be summarized using frequency counts and percentages. Exact confidence intervals for point estimates may be provided. Statistical testing will be one-sided with a significance level of 0.025 or two-sided significance level of 0.05 unless specify otherwise. Data listings of individual subject data may be provided.

Subjects with washout and those without washout will be analyzed separately.

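### Enrolling the higher-IOP eye when both eyes qualify in the no-washout stratum builds regression to the mean into any IOP change from that reading; the size is unknown and probably modest

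*Combined protocol and SAP*

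**What the plan says.** Section 8.5 sets the study eye differently in the two strata.

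- **No washout:** "if both eyes qualify, the eye with higher pre-operative medicated IOP should be enrolled". For ties, "If both eyes have same pre-operative medicated IOP, right eye should be enrolled".
- **Washout:** "the eye that received OMNI surgery post medication washout should be enrolled". The two eyes are not ranked by IOP.

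Other sections bear on how the chosen reading is used:

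- The synopsis schedule lists the retrospective visits as "Subjects without a medication washout: Preoperative, Surgical", so one pre-operative visit is evident in this stratum.
- Section 10.4 states "Confidence intervals for change from baseline will be included for selected endpoints" and "Subjects with washout and those without washout will be analyzed separately".
- Section 8.3 caps the stratum: "up to 50 subjects will be enrolled for whom there was no pre-surgery washout".
- Section 8.4 states "The pre-operative and surgery data (and in some cases, depending on enrollment date, Month 6 and Month 12) will be collected retrospectively".
- Section 18.4 leaves the retrospective IOP method to the investigator. Prospective visits use the mean of two readings or the median of three.

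The effectiveness endpoint list, the eligibility criteria and Tables 1 and 2 are not in the public text.

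**The concern.** A recorded IOP is the eye's usual pressure plus measurement error and visit-to-visit variation. The higher of two such readings has, on average, a positive error. That error does not persist, so later readings in the chosen eye tend to be lower whether or not the surgery worked. If the reading used to choose the eye is also the baseline, the mean change and its confidence interval shift in the device's favour, and a larger sample does not remove the shift. No control arm is described, and the strata are analysed separately, so neither a comparator nor the washout stratum offsets it.

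Two links are inferred. The first is that the selection reading is the baseline, because only one pre-operative visit is listed. The second is that IOP change is among the selected endpoints. This is likely for a device indicated to reduce IOP, but it is not shown.

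The rule does not affect subjects with one qualifying eye, the washout stratum or the primary safety endpoint.

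**Working it through.** The visible text has no variance, effect size or sample-size figure to reproduce. Only the cap of 50 comes from the documents. The other inputs are assumptions:

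| Input | Assumed values |
|---|---|
| e, SD of reading error in one eye | 1.5, 2, 2.5 mmHg |
| d, SD of the true between-eye difference | 1, 1.5, 2, 2.5, 3 mmHg |
| rho, between-eye correlation of errors | 0, 0.25, 0.5 |
| SD of IOP change | 3, 4, 5 mmHg |
| Share of subjects with two qualifying eyes | 10%, 30%, 50% |

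**Step 1: spurious fall per subject with two qualifying eyes.**

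Bias = [e²(1 − rho) / sqrt(d² + 2e²(1 − rho))] × sqrt(2/pi)

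- Working case (e = 2, d = 1.5, rho = 0.25): 4 × 0.75 = 3; sqrt(2.25 + 6) = 2.872; 3 / 2.872 × 0.798 = **0.83 mmHg**.
- Same case with d = 2: 0.76. With d = 3: 0.62.
- All 45 combinations: 0.27 to 1.36, median 0.71.
- If the chart value were a mean of two or three readings with independent errors (e divided by sqrt 2 or sqrt 3), the working case falls to 0.52 or 0.39.

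A separate derivation split each eye's deviation into a stable and a transient part. It gave 0.18 to 1.41 mmHg over a slightly wider range of inputs. Simulation with whole-mmHg readings and the right-eye tie rule agreed with that formula to within 0.02 mmHg.

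**Step 2: shift of the stratum mean.** Shift = share × bias. The standard error of the mean change is SD / sqrt(50), which is 0.42, 0.57 or 0.71 at SD 3, 4 or 5.

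| Share | Shift, working case (range), mmHg | In SEs, working case, SD 4 | Coverage of nominal 95% CI, working case, SD 4 |
|---|---|---|---|
| 10% | 0.08 (0.03–0.14) | 0.15 | 95% |
| 30% | 0.25 (0.08–0.41) | 0.44 | 93% |
| 50% | 0.42 (0.13–0.68) | 0.74 | 89% |

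No combination exceeds one standard error at a 10% or 30% share. At 50%, 16 of 45 do so at SD 3, 5 of 45 at SD 4 (all with e = 2.5) and none at SD 5. In the working case the shift reaches one standard error at shares of 51%, 68% and 85% for SD 3, 4 and 5.

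**Step 3: interaction with an entry threshold.** Any IOP cut-off would add its own regression to the mean. In an illustration (assumed mean 20, between-subject SD 3, both eyes reading at least 20, working case), the spurious fall is 1.41 mmHg under the current rule and 0.73 under a right-eye rule. The rule itself therefore adds 1.41 − 0.73 = 0.68.

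**Step 4: an upper limit from the study's own data.** Half the mean absolute between-eye difference in the selection readings bounds the bias per two-eye subject in expectation, provided the higher-reading eye is not truly lower on average. In the working case it is 0.5 × 2.872 × 0.798 = 1.15 mmHg against a true 0.83; at d = 3 it is 1.55 against 0.62. It is conservative, and it held at all 45 combinations and in 24 simulated settings with whole-mmHg readings, with and without cut-offs. Its working-case standard error is 0.39, 0.22 or 0.17 mmHg with 5, 15 or 25 two-eye subjects.

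**The case against.** The main objections are these:

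- **Both premises rest on text that is not shown.** A separate baseline definition or a second pre-operative reading could sit there. This stands, and it is why the finding remains conditional. The visible visit list and the planned change-from-baseline intervals make the premises likely.
- **The effect may be small.** At a 10% share it is negligible. A high share needs both eyes to be pseudophakic with mild to moderate disease and to have had standalone surgery without washout. The documents give no share, so 50% is not supported. This stands.
- **The working case sits slightly above the centre of the grid.** It is 0.83, against 0.76 at d = 2 and a median of 0.71. At the median, the shifts for 30% and 50% shares at SD 4 are 0.38 and 0.63 standard errors instead of 0.44 and 0.74. True, but neither the direction nor the description as modest changes.
- **The present rule has merit.** It is fixed in advance and uses only pre-operative data. That matters because Month 6 and Month 12 outcomes may already be charted at enrolment. A right-eye rule keeps this property.
- **The fix is partial.** It leaves any bias from an entry threshold, and a change in mid-enrolment would mix two rules. Both points stand. The second is why a reporting fallback is needed.

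**Conclusion.** The concern holds as a conditional one. If the reading that selects the eye is also the baseline for IOP change, the no-washout stratum will show a fall that the surgery did not cause. The direction follows from the rule. The size cannot be known from the documents. It is probably modest: roughly 0.03 to 0.68 mmHg in the stratum mean over the assumed ranges and shares of 10% to 50%, and above one standard error only at a high share with less favourable assumptions. It does not threaten the primary safety endpoint. Priority is minor to moderate, and the case for changing rests mainly on how little the change costs.

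**What to change.** **If enrolment is still open.** In section 8.5, for no-washout subjects only, replace the IOP ranking with the existing tie-break: when both eyes qualify, take the right eye. This is fixed in advance, cannot be steered by outcomes already in the chart, and removes the bias that the ranking adds. It costs one sentence and no subjects or visits. The mean baseline IOP and the reported reduction would be slightly smaller.

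**If eyes are already enrolled.** Leave the selection alone and report:

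1. B, the number of the n no-washout subjects who had two qualifying eyes.
2. Half the mean absolute between-eye difference in the readings used to apply section 8.5, and B/n times that value as an upper limit on the shift. This needs the fellow eye's pre-operative reading. Sites must already look it up to apply the rule, but the visible text does not say that it is recorded.
3. IOP change in one-eye subjects, as a descriptive sensitivity analysis only. At SD 4 its standard error is 0.60, 0.68 or 0.80 mmHg with 45, 35 or 25 subjects, and these subjects may differ in other ways. A one-eye against two-eye comparison has a standard error of 1.13 to 1.89 mmHg over the same splits of 50, so it cannot show whether the rule mattered.
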